4.2.3 Rationale for estimand

Intercurrent events have been identified within the estimands for this study because of their potential to impact efficacy assessments linked with the primary and secondary study objectives. In order to account for the effect of any observed post-randomization intercurrent events on the efficacy analyses, the following estimand strategies will be implemented when evaluating the primary and secondary efficacy endpoints:

- A composite estimand strategy will be used for the primary analysis of the primary and binary secondary endpoints (HiSCR₅₀, HiSCR₇₅, HS worst skin pain response).
- A hypothetical estimand will be used for the primary analysis of the continuous secondary endpoints (CFB in DLQI total score and in “worst skin pain” item for the HSSDD).

4.2.3.1 Composite estimand

A composite estimand strategy as defined in Section 8.2.2 allows incorporation of the two intercurrent events (eg, receipt of systemic antibiotic rescue medication or discontinuation of study treatment due to an AE or lack of efficacy) within the definition of the endpoint. These intercurrent events are considered meaningful to the efficacy outcome following receipt of study medication. For example, within the proposed composite estimand framework, a randomized study participant who discontinues from study treatment due to lack of efficacy prior to Week 16 will be considered a treatment failure at Week 16 regardless of the lesion count assessment performed at that visit.

The assumptions and robustness of the primary analysis (modified composite estimand as defined in Section 8.2.2) will be assessed through the sensitivity analyses defined in Section 8.2.3. The impact of intercurrent event handling and data imputation methods on endpoint derivation will also be assessed via the analyses of lesion counts and derived HiSCR variables as specified in Section 8.4.2.1 and Section 8.4.1.1, respectively.

4.2.3.2 Hypothetical estimand

The hypothetical estimand is defined in Section 8.3 and involves a data-driven approach to account for the potential impact of intercurrent events (eg, receipt of systemic antibiotic rescue medication or discontinuation of study treatment due to an AE or lack of efficacy) on the analysis of continuous efficacy endpoints. Under this framework, outcomes for study participants without an intercurrent event are analyzed as observed. Conversely, outcomes for study participants with an intercurrent event are imputed via a multiple imputation model, ie any

recorded data on or after the intercurrent event will be set to missing and imputed via multiple imputation following the strategy established in Section 4.2.2.1.

4.2.4 Dates and times

For analyses of AEs and concomitant medication usage, a complete date is required in order to correctly identify the AE or medication as occurring during treatment or not, and for correctly assigning an AE or concomitant medication to the Initial Treatment Period or Maintenance Treatment Period.

For purposes of imputing missing components of partially-reported start and stop dates for AEs and for medication use, the algorithms listed below will be followed. Start and stop dates of AEs or concomitant medication will be displayed as reported in the participant data listings (ie, no imputed values will be displayed in data listings).

Partial AE and concomitant medication start dates will be imputed as follows:

- Imputation of Partial Start Dates
 - If only the month and year are specified:
 - If the month and year of first dose of study medication is the same as the month and year of the partial start date, then use the date of first dose of study medication,
 - Else, if the month and year of the partial start date are the same as the month and year of a study medication switch date, then use the date of study medication switch,
 - Otherwise, use the 1st of the month of the partial start date;
 - If only the year is specified:
 - If the year of first dose of study medication is the same as the year of the partial start date, then use the date of first dose of study medication,
 - Else, if the year of the partial date is the same as the year of a study medication switch date, then use the date of study medication switch,
 - Otherwise, use the 1st of January of the year of the partial start date;
 - If the start date is completely unknown:
 - If the stop date is unknown or not prior to the date of first dose of study medication, then use the date of first dose of study medication,
 - If the stop date is prior to the date of first dose of study medication, then use the 1st of January of the year of the stop date.
- Imputation of Partial Stop Dates
 - If only the month and year are specified, :
 - Use the last day of the month of the partial stop date;
 - If only the year is specified
 - use December 31st of the year of the partial stop date;
 - If the stop date is completely unknown,

- Do not impute the stop date.

Note that if the stop date or the imputed stop date is prior to the imputed start date, then follow the procedure outlined below:

- If only the year of the start date is specified:
 - If the year of start date is the same as the year of first dose of study medication and the imputed stop date is after the date of first dose of study medication, then set the start date to the date of first dose of study medication,
 - Otherwise, set the 1st January of the year of the start date;
- If only the month and year of start date are specified:
 - If the month and year of the start date is the same as the month and year of first dose of study medication and the imputed stop date is on or after the date of first dose of study medication then set the start date to the date of first dose of study medication,
 - If the month and year of the start date is the same as the month and year of first dose of study medication and the imputed stop date is before the date of first dose of study medication then set the start date to the 1st of the month of partial start date.

Missing start times for medications will be imputed as 00:00h or with the time of dosing for events occurring on the date of IMP administration in case of missing hour and minute.

Otherwise start times with only missing minutes will be imputed with :00 or with the minutes of dosing for events occurring on the date and hour of IMP administration.

In the event of ambiguity or incomplete data that makes it impossible to determine whether a medication was concomitant or an AE was treatment emergent, the medication will be considered as concomitant or the AE will be considered treatment emergent. Similarly, in the event of ambiguity or incomplete data which makes it impossible to determine whether a medication or AE is to be assigned to the Initial Treatment Period or to the Maintenance Treatment Period (or both, for medications), then the medication will be assigned to both Treatment Periods, and the AE will be assigned to the Initial Treatment Period.

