2.3.2.2 Initial Treatment Period (Weeks 0-16) and Maintenance Treatment Period (Weeks 16-48)

Eligible study participants will be randomized in a 2:2:2:1 ratio as noted in the Study Schema to:

- Bimekizumab 320mg Q2W from Weeks 0 to 48
- Bimekizumab 320mg Q4W from Weeks 0 to 48
- Bimekizumab 320mg Q2W to Week 16, continuing on 320mg Q4W from Weeks 16 to 48
- Placebo to Week 16, continuing on bimekizumab 320mg Q2W from Weeks 16 to 48

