3.9 Definition of an intercurrent event

Handling of intercurrent events is one of the key elements for the analysis of efficacy endpoints.

An intercurrent event is defined as receipt of systemic antibiotic rescue medication or discontinuation of study treatment due to an AE or lack of efficacy (See Section 8.2.2).

Receipt of systemic antibiotic rescue medication is defined as initiating any systemic antibiotic on or after Baseline for any reason (including in response to an AE). The only exception to this rule is if a participant randomized to the antibiotic stratum on a tetracycline antibiotic interrupts their stable dose of tetracycline antibiotic during the study and subsequently restarts the same tetracycline antibiotic as confirmed using the coded preferred term. The restarted dose and frequency of the antibiotic must be the same or lower than the regimen prior to the interruption.

The dates of an intercurrent event are as follows:

- For receipt of systemic antibiotic rescue medication: start date of the antibiotic
- For discontinuation of study treatment due to an AE or lack of efficacy: Last study treatment date + 17 days. Note: study treatment discontinuation includes study discontinuation.

The choice of 17 days is intended to capture the interval between dosing and lesion assessments (14 days), as well as the visit window (3 days).

An additional sensitivity analysis will be conducted where missing data due to COVID-19 will be considered an intercurrent event and will be imputed as a nonresponse at that particular visit. This will be identified when there are missing data at a visit that has been impacted by COVID-19 according the COVID-19 impact CRF page. The date of this intercurrent event will be the date of the impacted visit.

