6.4.2 Classification of participants as analgesic, antihistamine users

If a participant has taken a new analgesic/increased regimen of analgesic, or taken an antihistamine, on 1 or more days (need not be consecutive) in a study period (Initial Treatment Period or Maintenance Treatment Period), then for that period the participant will be classified as an analgesic or antihistamine user, respectively. The period under consideration is to match the period as defined for the HSSDD for the Initial Treatment Period or HSSQ for the Maintenance Treatment Period, based on dates/times of the medications taken.

New analgesic/increased regimen of analgesic use, regardless of indication, is defined as an analgesic medication with start date on or after the first dose of study medication. Stable analgesics (ie, analgesics which were taken already before randomization) will not be included in this category of analgesic user. This classification will be used for selected subgroup analyses.

Antihistamine use is identified by considering the ATC classification. This classification is used for analyzing the Worst Itch endpoint and for selected subgroup analyses, by visit, for the Initial Treatment Period and Maintenance Period as applicable.

Additionally, if a participant has taken a new analgesic/increased regimen of analgesic on 1 or more days (need not be consecutive) prior to the Week 16 visit, then for that week the participant will be classified as an analgesic user. This classification will be used to adjust the formal analysis of the Worst Skin Pain secondary endpoints. If there is a visit date but no HSSDD available at the visit, then the analgesic/antihistamine user status for that week will be derived based on the visit date. If there is no visit available, then the weekly analgesic/antihistamine user status will default to the analgesic/antihistamine status for the overall study period.

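### Partial medication start dates in the Week 16 month are imputed differently by arm, because only two of the four arms have a switch date (SAP Section 4.2.4)

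*SAP*

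**What the plan says.** Section 4.2.4 gives a single algorithm for both kinds of record: "Partial AE and concomitant medication start dates will be imputed as follows". Section 6.4 sends medications there for partial dates.

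With month and year known, the first-dose date is used if the month matches. The next step applies "if the month and year of the partial start date are the same as the month and year of a study medication switch date" and assigns the switch date. The last step is "Otherwise, use the 1st of the month of the partial start date".

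With only the year known, the first-dose year is checked first. If the switch year matches instead, the switch date is assigned. The last step is "Otherwise, use the 1st of January of the year of the partial start date".

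The term for the switch date is not defined. Section 2.3.2.2 shows which participants have one. Two arms keep a single regimen throughout, for example "Bimekizumab 320mg Q4W from Weeks 0 to 48". The other two, Placebo/Q2W and Q2W/Q4W, change at Week 16.

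Two later sections depend on medication dates. Section 3.9 dates the antibiotic intercurrent event thus: "For receipt of systemic antibiotic rescue medication: start date of the antibiotic". Section 6.4.2 makes a participant an analgesic user, for the covariate in the pain analyses, if a new or increased analgesic was taken "on 1 or more days (need not be consecutive) prior to the Week 16 visit".

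**The concern.** A rule for completing a partial date should not depend on randomized treatment when the completed date feeds an efficacy comparison. Here it does. The middle step is available to two arms, and the other two drop to the last step, which always gives the same or an earlier date.

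The pooled Q2W group shows this most plainly. Section 3.6 combines Q2W/Q2W and Q2W/Q4W for the Initial Treatment Period, when their treatment is the same. Yet the same incomplete record gets a Week 16 date in one half and the 1st of the month in the other. A switch step is sensible for attributing an AE to a treatment. It has no such purpose for an antibiotic or analgesic that defines an efficacy variable up to Week 16.

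**Working it through.** **Inputs.** The algorithm is Section 4.2.4 as written and the arms are those in Section 2.3.2.2. Let F be the first-dose date, W = F + 112 days the Week 16 date, and d the day of the month of W. My assumptions are exact 112-day timing, the Week 16 dose given on the visit day, and F uniform over a four-year calendar (1,461 days, 48 months). The SAP states no figure to reproduce.

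**Size of the date difference**

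1. *Month and year known, month of W.* Switching arms get W and the others get the 1st, so the gap is d − 1 days. The range is 0 to 30 and the mean over the calendar is 14.7. Example: F = 1 March 2021, W = 21 June 2021, start recorded as June 2021. Placebo/Q2W gets 21 June and Q4W/Q4W gets 1 June, 20 days apart.
2. *Year only.* A gap arises only if W falls in the year after F, which happens for 112 × 4 / 1,461 = 31% of first-dose dates. It runs from 0 to 111 days, mean 111/2 = 55.5. Example: F = 16 November 2020, W = 8 March 2021, start recorded as 2021. Placebo/Q2W gets 8 March and Q4W/Q4W gets 1 January.
3. *Everything else.* The first-dose month and every month other than that of W give the same date in all arms. With true starts uniform from Day 1 to Week 16, about 14% of month-and-year dates are affected.

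**Where a switch-month date matters**

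- *Analgesic covariate (Sections 6.4.2, 8.3.3.1, 8.3.4.1).* The cut is strictly before the Week 16 visit. A record dated on W does not count; one dated on the 1st does, unless W is itself the 1st. Status differs in 1 − 48/1,461 = 97% of switch-month records.
- *Intercurrent-event status at Week 16.* Sections 4.2.1, 4.2.1.2 and 8.2.2 include the visit itself. Both W and the 1st are on or before W, so every arm counts the event and the difference is zero.
- *Status at a visit 14 days earlier.* It differs when d ≥ 15: (1,461 − 48 × 14)/1,461 = 54%.
- *Status at Week 12, where Section 8.5 places nominal tests.* It differs only when d ≥ 29: (1,461 − 48 × 28)/1,461 = 8%.
- *Time to flare, rescue and intercurrent event (Sections 8.4.5, 8.4.11, 8.4.12).* In the June example an antibiotic event falls on day 112 + 1 = 113 for Placebo/Q2W and day 92 + 1 = 93 for Q4W/Q4W. For time to flare this applies if no flare came first.

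**Does another rule repair it?** The closing paragraph of Section 4.2.4 settles only whether a medication is concomitant and which period it belongs to; it does not settle the start date. The correction for a stop date before the imputed start covers month-and-year dates only in the first-dose month. A switching participant whose known stop date precedes W in that month therefore keeps a start after the stop.

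**The case against.** The strongest objection is that little of confirmatory importance is touched, and much of that stands.

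- *Primary endpoint.* Table 8-1 and part of Section 8.2.2 describe intercurrent events as occurring before Week 16. A reader might infer that one record makes a Q4W participant a failure and leaves a placebo participant a responder. The operative text does not support this. Response requires no event through Week 16 (Section 8.2.2), nonresponse starts at the time point of the event (Section 4.2.1.1), and the continuous and observed-case rules count events on or before the visit (Sections 4.2.1.2, 8.2.3.5).
- *Known bias.* A reader might infer a consistent bias against the non-switching arms. That also fails. Values after an event are imputed for continuous endpoints (Section 4.2.3.2), time to HiSCR is censored at the event (Section 8.4.1.2), and a changed covariate value has no fixed effect on the treatment estimate. Where the direction is clear, as in time to rescue, it runs against bimekizumab.
- *Blinding.* Needing the treatment code is not in itself a defect. Other derivations depend on arm, such as the Q4W dosing interval in Section 10.1.1.1 and the Week 16 antibody baseline for placebo in Section 9.3.2.
- *Undefined term and inferred link.* The sponsor may mean the first Maintenance dose for everyone, in which case the difference vanishes. But Sections 9.3.2 and 10.2.1 use switch for a change of treatment. Sections 3.9 and 6.4.2 do not cite Section 4.2.4, so its use there is an inference, though it is the only partial-date rule for medications in the SAP.

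What the objection does not answer is the strict analgesic cut, or why identically treated participants should be dated by different rules.

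**Conclusion.** The point holds in a limited form. For partial dates in the switch month, and year-only dates in a switch year that differs from the first-dose year, the imputed medication start depends on arm. The difference is 0 to 30 days (mean about 15) in the first case and 0 to 111 days in the second.

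It reaches the analgesic covariate of the two confirmatory pain analyses, intercurrent-event status before Week 16, and three log-rank comparisons outside the controlled testing sequence. It does not reach Week 16 intercurrent-event status for the primary or secondary endpoints.

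The SAP does not say how many records are partial, so no effect on any result can be computed; it is probably small. The conclusion rests on reading the switch date as the participant's own change of treatment, and on Section 4.2.4 governing the dates used in Sections 3.9 and 6.4.2. This is a low-priority correction, worth making because the rule has no efficacy rationale and is easily replaced.

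**What to change.** In Section 4.2.4, for concomitant medications, use the same anchor in all four arms. Either replace the switch date with the date of the first Maintenance Treatment Period (Week 16) dose for every participant, or delete the switch step so that all arms use the 1st of the month or 1 January. Either choice makes the difference between arms zero by construction, and the dates can then be derived without the treatment code. If the Week 16 anchor is chosen, extend the stop-before-start correction to that month.

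The cost is one wording change and the matching program edit. There is one small downside. If the AE rule stays as it is, an AE and the medication treating it can receive different imputed dates from the same partial month. Applying the common anchor to AE start dates as well avoids this.

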4 STATISTICAL/ANALYTICAL ISSUES

4.1 Adjustments for covariates

The primary efficacy analyses and selected secondary analyses will be adjusted for the 2 randomization stratification variables:

- Hurley Stage at Baseline (II or III)
- Baseline antibiotic use (Yes or No)

If a participant is stratified in the incorrect stratum (ie, the stratum recorded in the Interactive voice or web Response System differs from the actual stratum the participant belongs to), the actual stratum will be used for the analysis.

The continuous secondary endpoints will also include the Baseline value as a covariate.

The Worst Skin Pain secondary endpoints (change from Baseline continuous endpoint and pain response binary endpoint) will also include analgesic use as a covariate.

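### If start dates imputed under Section 4.2.4 feed the rescue rule in Section 3.9, a stable Baseline antibiotic with certain incomplete dates becomes a Day 1 intercurrent event

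*SAP*

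**What the plan says.** **Date rule (SAP 4.2.4).** The imputation algorithms apply to adverse events and medication use. A start date becomes the date of first dose in three cases:

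- month and year are known and match those of first dose;
- only the year is known: "If the year of first dose of study medication is the same as the year of the partial start date";
- the start is completely unknown: "If the stop date is unknown or not prior to the date of first dose of study medication".

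A year-only date that matches neither the first-dose year nor the year of a treatment switch falls to the last branch: "Otherwise, use the 1st of January of the year of the partial start date".

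**Rescue rule (SAP 3.9).** Receipt of rescue is "defined as initiating any systemic antibiotic on or after Baseline for any reason (including in response to an AE"), and the event is dated by the start of the antibiotic. One exemption is given: "The only exception to this rule is if a participant randomized to the antibiotic stratum on a tetracycline antibiotic interrupts their stable dose" and later restarts the same drug at the same or a lower regimen.

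**Consequences (SAP 4.2.1.1, 4.2.1.2, 4.2.3.2).** After an intercurrent event the primary and binary secondary endpoints are nonresponse from that point on, even where lesion counts or scores were observed. For the continuous secondary endpoints the recorded data are set to missing and imputed.

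**The concern.** The trial stratifies randomization by current antibiotic use, so participants on a stable systemic antibiotic are expected. Section 6.4 classes a drug that began before first dose and continued as both prior and concomitant. It refers to Section 4.2.4 for incomplete dates, and it also tabulates the antibiotics that qualify as intercurrent events.

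Moving an uncertain start to Day 1 is harmless for a concomitant medication table, because an ongoing drug is concomitant either way. It is not harmless when the question is whether the drug is new, because the imputation then creates the very fact being tested. A participant with an observed response could be scored a failure on the primary endpoint because a day or month was not recorded.

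Most sensitivity analyses of HiSCR50 would carry the same error. The NRI, reference-based, FAS, PPS, COVID-19 Free Set, COVID-19-event and CMH analyses all keep the composite strategy, and the observed-case analysis drops the participant. The treatment policy analysis does not depend on the event. The rescue and time-to-event summaries in Sections 8.4.10 to 8.4.12 would count false Day 1 events.

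**Working it through.** **1. Applying the date rules.** Take an illustrative first dose on 15 September 2021 and an antibiotic that is still ongoing:

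| Recorded start | Start under 4.2.4 | Rescue under 3.9 if that date is used? |
|---|---|---|
| 2021 | 15 Sep 2021 | Yes, Day 1 |
| Sep 2021 | 15 Sep 2021 | Yes, Day 1 |
| completely unknown | 15 Sep 2021 | Yes, Day 1 |
| Aug 2021 | 1 Aug 2021 | No |
| 2020 | 1 Jan 2020 | No |

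**2. Looking for something that stops it.**

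- The exemption in 3.9 needs an interruption and restart of a tetracycline. An uninterrupted antibiotic does not qualify.
- The correction in 4.2.4 for a stop date before the imputed start cannot apply to an ongoing drug.
- The tie-break at the end of 4.2.4 settles only concomitant status, treatment emergence and study period, not whether a drug is new.
- Section 6.4.2 keeps analgesics already taken before randomization out of its new-use category. Section 3.9 has no such provision for antibiotics.

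**3. The plan's own power figure.** Inputs from Section 2.4 and Table 2-1: HiSCR50 0.50 on Q4W (n = 140) and 0.25 on placebo (n = 70), two-sided alpha 0.025 (z = 2.2414).

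Power = Φ[(d − z·SE0)/SE1], where SE0 uses the pooled rate and SE1 the separate rates.

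- Pooled rate = (140 × 0.50 + 70 × 0.25)/210 = 0.4167
- SE0 = √[0.4167 × 0.5833 × (1/140 + 1/70)] = 0.0722
- SE1 = √[0.50 × 0.50/140 + 0.25 × 0.75/70] = 0.0668
- Power = Φ[(0.25 − 2.2414 × 0.0722)/0.0668] = Φ(1.32) = 0.907, against the stated 0.90

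**4. Effect of false failures.** Suppose a share f of every arm is wrongly failed, and those participants would otherwise respond at their arm's rate. Each rate is then multiplied by (1 − f).

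| f | Q4W | Placebo | Difference | Odds ratio | Power |
|---|---|---|---|---|---|
| 0 | 0.500 | 0.2500 | 0.2500 | 3.00 | 0.907 |
| 3% | 0.485 | 0.2425 | 0.2425 | 2.94 | 0.890 |
| 6% | 0.470 | 0.2350 | 0.2350 | 2.89 | 0.872 |

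**5. Plausible f.** The SAP gives neither the size of the antibiotic stratum nor the rate of incomplete dates. As an assumption, let 10% to 30% be on a Baseline antibiotic and 5% to 20% of those have a start date that triggers the rule:

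- low: 0.10 × 0.05 = 0.5%, and 490 × 0.005 = 2.5 participants
- high: 0.30 × 0.20 = 6%, and 490 × 0.06 = 29.4 participants

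**The case against.** The strongest reply is that the SAP never explicitly joins the two sections. Section 4.2.4 gives its purpose as placing events and medications on or off treatment and in a period, Section 3.9 does not cite it, and a drug known to be in use at Baseline was not initiated then. A careful programmer could reach the right answer. This stands, and it is why the point is conditional. It does not dispose of it: 4.2.4 is the only rule for incomplete medication dates, 3.9 dates the event by the start date, and two programmers could derive different primary endpoints from the same text.

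It is also fair that the plan's outputs could expose the error. Baseline antibiotic use is summarized both as randomized and as derived. HiSCR is also shown without intercurrent-event imputation, and the time-to-event curves would drop on Day 1. Detection at that stage, however, may come after unblinding.

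The month-match case is narrow. Screening lasts at least 14 days, so a drug in use when Screening begins can match only if first dose falls on day 15 of the month or later.

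A reader might infer two further problems that the document does not support.

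- The derived Baseline antibiotic status might be thought to flip to no. The SAP does not say how that status is derived, so this is conjecture.
- The exemption in 3.9 refers to the randomized stratum, whereas Section 4.1 says "the actual stratum will be used for the analysis". That sentence concerns covariate adjustment and does not contradict 3.9. The case in which it would matter needs a mis-stratified participant who also interrupts and restarts a tetracycline, which is marginal.

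**Conclusion.** The point holds conditionally. Taken as written, Section 4.2.4 gives an ongoing Baseline antibiotic a Day 1 start in three cases, and nothing in Section 3.9 prevents that date from making it rescue.

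It would be too strong to say that every incompletely dated Baseline antibiotic is affected, since an earlier year or an earlier known month stays before Baseline. It would also be too strong to say that such participants fail on every endpoint. Only the responder endpoints become failures. For DLQI and pain change the cost is the loss of all post-Baseline observations, replaced by imputed values.

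The size is unknown from the SAP and probably small. Even at the 6% corner of the assumed range, Q4W power for HiSCR50 loses 3.5 points (0.907 to 0.872) and the odds ratio moves from 3.00 to 2.89. Those figures rest on an even spread over arms. That is reasonable, because antibiotic use is a stratification factor and a pre-Baseline start date should not depend on the arm. Under that assumption the pull is towards no difference, so a false positive is not the worry. The case for acting is that the primary endpoint should not depend on how one programmer reads an unlinked date rule.

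**What to change.** Add to Section 3.9:

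> A systemic antibiotic documented as in use before first dose is not treated as initiated on or after Baseline because of a start date imputed under Section 4.2.4. Antibiotic records with a partial or unknown start date are classified by blinded review before unblinding. Restarts and dose increases remain subject to the existing rule in this section.

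The last sentence keeps the current regimen condition for restarts intact. A rule that exempted any record matching the antibiotic named at stratification should be avoided, because it could let a restart at a higher regimen escape that condition. No change to the stratum wording of the exemption is needed.

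The cost is one paragraph, one derivation flag and a blinded look at what is likely to be a small number of records. The downside is that a truly new antibiotic whose start date cannot be resolved could occasionally be missed as rescue.
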